3.3 Study design

This is a monocentric open label explorative study (with primary objective to assess the predictive value of daily steps for MACE). Patients will be asked to wear an activity tracker for two weeks following hospital discharge. Patients who participate in any form of CR in our institution and attend the routine check-up 12 month after PCI in our institution will be asked to wear the activity tracker again for two weeks.

3.4. Study intervention

Patients will be informed about the study by the prevention team (advanced nurse practitioners) usually on the day of discharge from PCI during the routine visit by this team to inform patients about the different options of CR. Patients will be provided with an activity tracker in the form of a wrist band, the patient information sheet including informed consent (IC), the IPAQ-SF and an addressed and prepaid envelope. They are asked to read the patient information when arrived at home, sign the IC when willing to participate and wear the wrist band continuously for two weeks after hospital discharge. After that, they should send the wrist band, the filled in IPAQ-SF and signed IC in the provided envelope to our institute. If they are unwilling to participate, they can send the activity tracker back straight away. Patients attending the clinical routine check-up after 12 months in our institution will be asked to wear the activity tracker again for two weeks.

4 STUDY POPULATION AND STUDY PROCEDURES

4.1 Inclusion and exclusion criteria, justification of study population

Approximately 800 consecutive patients after PCI who are informed about different forms of CR are recruited for this study.

Study inclusion criteria:

- 18-79 years of age;
- eligible for ambulatory CR (not living in nursing home, not enrolling in stationary CR).

Exclusion criteria:

- Staged PCI;
- previous participation in this study;
- inability or contraindications to undergo CR (nursing home residence, stationary CR, orthopedic or neurologic impairment prohibiting physical exercise, psychiatric conditions)
- inability to follow the procedures of the study, e.g. due to language problems, psychological disorders, dementia, etc..

4.2 Recruitment, screening and informed consent procedure

Consecutive patients who are eligible for ambulatory CR are seen by the prevention team (nurse practitioners) usually on the day of hospital discharge from PCI and will be informed about the different forms of CR and the study.

All eligible patients will be provided a participant information sheet and a consent form describing the study and providing sufficient information for participants to make an informed decision about their participation in the study. The participants can consider their participation and decide upon participation during the first week after hospital discharge. Additionally to the patient information sheet and the IC form, the activity tracker in the form of a wrist band, the IPAQ-SF and an addressed and prepaid envelope will be handed out before hospital discharge. They are asked to read the patient information when arrived at home, sign the IC when willing to participate and wear the wrist band continuously for two weeks after hospital discharge. After that, they should send the wrist band, filled-in IPAQ-SF and signed IC in the provided envelope to our institute.

Each participant will be informed that if they lose the activity tracker or it is lost with the mail, they are not held reliable for the loss. Each participant will be informed that the participation in the study is voluntary and that he or she may withdraw from the study at any time and that withdrawal of consent will not affect his or her subsequent medical assistance and treatment.

The participant will be informed that his or her medical records may be examined by authorised individuals other than their treating physician.

The formal consent of a participant, using the approved consent form, will be signed by the participants at home and sent back with the questionnaire and activity tracker. The participants are not submitted to any study procedures other than wearing the activity tracker.

The consent form will be signed and dated by the investigator or his designee when the form arrives at the Inselspital. A copy of the signed informed consent will be sent back to the study participant. The consent form will be retained as part of the study records.

4.3 Study procedures

For each patient the study duration is two weeks during which the activity tracker is worn. Patients who complete their yearly follow-up at our institute are asked to wear the activity tracker again for

two weeks when they come to the follow-up visit.

Patient recruitment will last for 16 months, with first participant in October 2020, last patient recruited in February 2022 and last follow-up in April 2023.

4.4 Withdrawal and discontinuation

Data gathered until withdrawal of consent will be used in coded form. Wearing the activity tracker again after 12 month is voluntary. MACE data derived from CARDIOBASE registry is subject to the CARDIOBASE registry consent, in case of withdrawal of consent for CARDIOBASE MACE and patient related data from this registry will not be used. Health related data from the clinic's patient information system will not be used if patients withdrawal the study IC and the clinic's general informed consent.

5 STATISTICS AND METHODOLOGY

5.1. Statistical analysis plan and sample size calculation

Predictive value of daily steps during the first two weeks after hospital discharge is quantified by net reclassification improvement (NRI) and by increase of area under the curve (AUC) of the receiver operating characteristic curve (ROC) of a model consisting of traditional risk factors (age, sex, cardiovascular risk factors, cardiovascular history, comorbidities).

Descriptive statistics are used to quantify and characterise the populations who choose conventional hospital based CR, tele-rehabilitation, and modular CR in terms of number, age, sex, medical history, cardiovascular risk factors and comorbidities. MACE at one year follow-up and daily steps during the first two weeks after hospital discharge will be compared between the CR and non CR participants using multivariate modelling adjusted for potential confounding factors. Further, for patients who perform their yearly routine follow-up visit at our centre, data on body mass index (BMI), systolic blood pressure (BP), low-density lipoprotein cholesterol (LDL-C) and smoking cessation will be derived from the clinic's patient information system and compared between different forms of CR. Also, daily steps after 12 months from patients who volunteer to monitor steps again will be quantified for the different CR groups and tested between the groups if sufficient data can be gathered. The same will be done for changes in daily steps between the first two weeks after hospital discharge and at 12 months.

Sample Size:

Based on a study on nearly 9000 PCI patients, physical activity level assessed by the Duke Activity Status Index (DASI) questionnaire found a 4.8-fold increase in future risk of incident major adverse cardiac events at 3 years in the quartile with lowest DASI compared to the highest quartile.(6) The DASI score reclassified 15% of patients ($P<0.001$) beyond traditional risk factors in predicting future MACE.(6) In the approximately 6500 patients with obstructive CAD, the adjusted HR (adjusted for traditional risk factors and history of heart failure and peripheral arterial disease) for MACE in the lowest DASI quartile compared to the highest quartile was 2.66 (95% CI 2.16 to 3.27). According to this relative hazard, 33 events would be needed to reach a significance level of 0.05 and a power of 80% in these two quartiles. For the whole sample this would be 66 events. According to data from CARDIOBASE, in the 10 years from 2009-2018 1083 (8%) of patients younger than 80 years had a MACE between 7 and 365 days after PCI, which corresponds to approximately 100 MACE per year. During the last 3 years (Oct 2015 to Oct 2018), 3683 patients younger than 80 years were recruited for CARDIOBASE, which equates to approximately 1200 potential study patients per year. If we assume that 50% of these patients are willing to participate in our study (wear an accelerometer for 2 weeks after discharge), we could recruit about 600 patients per year, of whom approximately 48 (8%) will have a MACE within 12 months following PCI. To reach 66 MACE we will need to recruit 825 patients which will require

a recruitment period of approximately 16 months.

Statistical analyses will be performed by [name] (CAS in statistics of the University of Bern) using the software R.

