3 STUDY OBJECTIVES AND DESIGN

3.1 Primary objective and hypothesis

Quantification of physical activity (daily steps) during the first two weeks after hospital discharge as a predictor for MACE at one year.

Hypothesis I: Daily steps measured during the first two weeks after hospital discharge from PCI is a significant independent predictor additional to traditional risk factors for MACE at one year after PCI.

Secondary objectives and hypothesis

1. Comparison between daily steps and objectively measured activity counts (divided in time spent in moderate-to-vigorous activity, light activity and sedentary activity), as well as patient reported activity:

Hypothesis I: Objectively monitored activity counts two weeks after hospital discharge is significantly associated with daily step counts and self-reported activity level

Hypothesis II: Predictive value of daily step count during the first two weeks after hospital discharge is significantly better than the predictive value by patient reported physical activity for MACE at 12 months.

2. Association of daily steps after one year with reaching targets for systolic blood pressure, low-density lipoprotein cholesterol (LDL-C), body mass index (BMI) and glycated haemoglobin (HbA1c):

Hypothesis I: Patients with higher daily step counts during the first two weeks after hospital discharge have higher achievement rates of target levels at 12 months for blood pressure, body weight, blood lipids, and blood sugar.

3. Comparison of daily steps after hospital discharge and MACE between non cardiac rehabilitation (CR), conventional hospital based CR, tele-CR and modular CR participants.

Hypothesis I: Tele-rehabilitation and conventional CR patients achieve higher daily step counts (corrected for age, risk factors and comorbidities) at two weeks after PCI than patients who decline any form of CR.

Hypothesis II: Tele-rehabilitation and conventional CR patients a lower risk of MACE within one year than patients who decline any form of CR

4. Comparison of daily steps at one year after hospital discharge in different CR groups.

Hypothesis I: Tele-rehabilitation is not inferior to conventional ambulatory cardiac rehabilitation (CR) in increasing daily steps from two weeks after PCI to 12 months after PCI

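### No internal validation is planned for the primary NRI and AUC gain: with about 66 events the reported AUCs would be too high, and an uninformative step count would still show a positive NRI on average

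*SAP*

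**What the plan says.** Section 5.1, repeated in the synopsis, states that the value of daily steps "is quantified by net reclassification improvement (NRI) and by increase of area under the curve (AUC) of the receiver operating characteristic curve (ROC"). The comparator is "a model consisting of traditional risk factors (age, sex, cardiovascular risk factors, cardiovascular history, comorbidities"). Age and sex are single variables; the other three items are open categories, so the number of model terms is not given. The type of NRI and any risk categories are not given either.

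The primary hypothesis in section 3.1 is that daily steps "is a significant independent predictor additional to traditional risk factors for MACE at one year after PCI".

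The sample size in section 5.1 starts from an adjusted hazard ratio that "in the lowest DASI quartile compared to the highest quartile was 2.66 (95% CI 2.16 to 3.27"), from which "33 events would be needed to reach a significance level of 0.05 and a power of 80% in these two quartiles". It continues: "For the whole sample this would be 66 events", and "To reach 66 MACE we will need to recruit 825 patients".

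No section mentions a bootstrap, cross-validation, a split sample, shrinkage, external validation or any other correction for optimism.

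**The concern.** A model fitted to a set of patients discriminates better in those patients than in the next ones, and the gap widens as events per parameter fall. With 66 events it is 66/8 = 8.3 events per parameter for 8 predictors, 66/12 = 5.5 for 12 and 66/20 = 3.3 for 20. Adding any variable, even pure noise, also improves in-sample fit on average, so NRI and AUC gain need not centre on zero when steps are worthless.

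This matters because the intended use lies in future patients: the synopsis and section 7.1 want steps to identify high-risk patients for closer follow-up. Same-sample figures do not estimate performance there. How the primary performance measures are estimated belongs in section 5.1.

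**Working it through.** **1. The plan's own figures reproduce.** Schoenfeld, 1:1, two-sided 0.05 (sidedness is not stated, but two-sided reproduces the figure), power 80%:

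events = 4 × (1.960 + 0.842)² / (ln 2.66)² = 4 × 7.849 / 0.957 = 32.8, rounded up to 33. Power with 33 events is 0.802.

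Whole sample: 2 × 33 = 66. Patients: 66 / 0.08 = 825. Recruitment: 825 / 600 × 12 = 16.5 months. The 8% is the plan's own rate ("of whom approximately 48 (8%) will have a MACE within 12 months following PCI"). Section 5.2 drops non-compliant wearers from the primary analysis and adds patients only when they exceed 50. With 50 dropped, events would be (825 − 50) × 0.08 = 62, so 66 is not a conservative figure for what follows.

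**2. Planning effect per SD of steps.** For a normal variable the means of the extreme quartiles lie 2.542 SD apart, so ln(2.66) / 2.542 = 0.385 per SD (ratio 1.47). This was used as a log odds ratio. Half of it is 0.192.

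**3. Simulation.** From the plan: 825 patients, 8% events. Assumed: 8, 12 or 20 independent normal base predictors, base linear-predictor SD 0.75, logistic models fitted in the cohort, category-free NRI. There were 200 datasets per setting, each checked in 20,000 new patients, and bootstrap optimism correction used 15 resamples. Cells show same-sample / new patients / bootstrap-corrected means.

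| Predictors | Steps effect | Base AUC | AUC gain | NRI |
|---|---|---|---|---|
| 8 | none | 0.716 / 0.680 / 0.681 | 0.0025 / −0.0021 / −0.0014 | 0.084 / 0.005 / 0.025 |
| 8 | half | 0.712 / 0.678 / 0.677 | 0.0079 / 0.0045 / 0.0047 | 0.163 / 0.132 / 0.124 |
| 8 | planning | 0.719 / 0.678 / 0.684 | 0.0227 / 0.0231 / 0.0232 | 0.311 / 0.301 / 0.300 |
| 12 | none | 0.727 / 0.671 / 0.677 | 0.0024 / −0.0019 / −0.0009 | 0.099 / 0.007 / 0.041 |
| 12 | half | 0.730 / 0.669 / 0.681 | 0.0070 / 0.0049 / 0.0054 | 0.172 / 0.125 / 0.136 |
| 12 | planning | 0.726 / 0.668 / 0.674 | 0.0208 / 0.0238 / 0.0221 | 0.298 / 0.299 / 0.278 |
| 20 | none | 0.745 / 0.656 / 0.673 | 0.0025 / −0.0016 / 0.0001 | 0.093 / 0.009 / 0.034 |
| 20 | half | 0.742 / 0.655 / 0.667 | 0.0066 / 0.0056 / 0.0056 | 0.164 / 0.137 / 0.120 |
| 20 | planning | 0.745 / 0.654 / 0.671 | 0.0206 / 0.0258 / 0.0242 | 0.333 / 0.306 / 0.310 |

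**4. Reading the table.**
- Base AUC, same-sample minus new: 0.034-0.042 with 8 predictors, 0.056-0.061 with 12, 0.087-0.090 with 20. The extended model behaves alike. A separate run of 250 datasets gave 0.752 against 0.655 for the extended model with 20 predictors and no steps effect, a gap of 0.097.
- AUC gain, same-sample minus new: +0.004 to +0.005 with no effect, +0.001 to +0.003 at half the planning effect, −0.0004 to −0.005 at the planning effect.
- Category-free NRI with no effect: 0.08-0.10 against below 0.01.

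**5. Other NRI definitions, no steps effect** (further simulation, 8 to 20 predictors, 400 datasets per setting). Categories at 5/10/20%: 0.010-0.014 against about −0.003. A single cut at 8%: 0.004-0.006 against about −0.002. Both sets of cut-points are assumptions.

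**6. Test of the steps coefficient** (same simulation as step 5). The Wald test rejected in 3-4% of null datasets at nominal 5%, and power at the planning effect was 79-82%.

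**The case against.** Section 5.1 does not say that the models are fitted and assessed on the same patients; it is silent. The defect is an omission, not a wrong procedure set down in writing. That stands. The background section speaks of improving existing risk tools, so a published score might be meant as the base. That would not rescue the plan: a score with fixed coefficients carries no optimism while a fitted extension does, so the gain would be more inflated, not less.

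The largest optimism is in the AUCs themselves, whereas the planned measure is their difference, in which optimism largely cancels between nested models. This also stands. A bias of about 0.005 in the gain is well below its between-dataset SD of 0.014-0.017 at the planning effect. A reader might infer that the AUC gain is always inflated in favour of steps. The plan's own planning effect does not support this: there the bias is nil or slightly against steps.

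A reader might also infer that a worthless step count is likely to be declared a significant predictor. The documents do not support that. The hypothesis in section 3.1 is about independent prediction, and a test of the steps coefficient holds its level. An NRI z-test would be less reliable, but the plan names none.

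Section 3.3 calls the study explorative, which lowers the stakes but does not turn a same-sample AUC into an estimate for new patients.

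**Conclusion.** The point holds as an omission with measurable consequences. Followed as written, on the inferred in-cohort fitting, the plan would report AUCs roughly 0.03-0.04 too high with 8 predictors and 0.08-0.10 too high with 20. The NRI would be positive on average even for an uninformative step count: material if category-free (0.08-0.10), small with categories (about 0.01-0.02). The AUC gain is biased by about 0.005 at most, in a direction that depends on the true effect, and inference on steps as an independent predictor is essentially sound.

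These sizes rest on an assumed predictor count, an assumed NRI type, independent normal predictors and a true base AUC of about 0.65-0.68 in new patients. This is a cheap improvement to the reporting of performance, not a flaw that invalidates the study.

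**What to change.** In section 5.1 and the synopsis, state that:

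- the reported AUC of each model, the AUC gain and the NRI are bootstrap optimism-corrected, with every modelling step repeated in each resample;
- they carry bootstrap confidence intervals, the calibration slope of each model is reported, and apparent values are shown alongside;
- the hypothesis in section 3.1 is judged by the likelihood-ratio or Wald test of steps in the adjusted model, not by the NRI.

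The cost is a paragraph of text and a little more R code, with no new data. Reported AUCs will be about 0.03-0.10 less favourable. Correction is incomplete in two places: base AUC with 20 predictors (0.673 corrected against 0.656 in new patients with no steps effect), and the category-free NRI with no effect (about 0.02-0.05 remains). The second is a further reason not to let the NRI carry the hypothesis.

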aiming at including and randomising 300 CAD patients.(20) Similar results were found for tele-rehabilitation compared to conventional CR with regard to motivation for keeping a healthy lifestyle, depression, anxiety and quality of life in 136 randomly assigned cardiac patients.(21) A non-randomised observational study has compared 24 tele-rehabilitation patients with 53 matched patients performing conventional CR during a later time period and has found similar results for physical activity assessed by questionnaire and quality of life.(22)

Risk prediction for major adverse cardiovascular event (MACE)

For patients with cardiovascular disease many instruments are available to calculate a risk score in order to estimate a patient's risk for death or reoccurring events. The RISK-PCI Score can be used for prediction of one-year adverse cardiovascular events in STEMI patients after PCI.(23) The GRACE score allows an in-hospital mortality risk assessment of patients with acute myocardial infarction as well as mortality risk assessment for up to 3 years.(24) It takes into account age, heart rate, systolic blood pressure, creatinine, abnormalities of ECG or cardiac enzymes, and signs of heart failure. The SMART risk score predicts the 10-year risk for recurrent vascular events in patients with previous cardiovascular disease.(25) Additional to age, sex, systolic blood pressure and smoking status, it takes into account history of cardiovascular disease and diabetes, as well as laboratory results of lipid status, kidney function and inflammation.

Based on the predictive value of daily steps for risk prediction found in some recent studies in various patient groups after surgery, we aim to assess the value of daily steps in patients with recent PCI in improving currently used risk assessment tools for MACE. Further, we aim to monitor whether patients enrolling in CR have higher step counts and fewer MACE than those not enrolling in CR, and whether there is a difference with regard to step counts in patients enrolling in different types of CR (conventional hospital-based CR, tele-CR, module-based CR).

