8.2 Data recording and source data

Data from the activity trackers will be downloaded and stored in Redcap. Questionnaires on physical activity will be manually entered into Redcap.

At the end of the study, data from this study will be merged with data from Cardiobase PCI registry, namely data on patient anthropometrics, cardiovascular history, indication for and interventions of the index PCI, comorbidities and cardiovascular risk factors, and MACE at one year follow-up. Data on choice of CR and compliance with CR and health related data will be available from the clinical data base of the unit for Preventive Cardiology and Sports Medicine of the Inselspital.

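### The base model for the primary analysis leaves out the indication for the index PCI, so the added predictive value of daily steps may be mis-stated in either direction

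*SAP*

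**What the plan says.** Section 5.1 states that the predictive value of steps "is quantified by net reclassification improvement (NRI) and by increase of area under the curve (AUC") over "a model consisting of traditional risk factors (age, sex, cardiovascular risk factors, cardiovascular history, comorbidities"). The synopsis repeats the same five groups.

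The primary hypothesis in section 3.1 is that early daily steps "is a significant independent predictor additional to traditional risk factors for MACE at one year after PCI". Section 2 gives a broader aim: to assess the value of steps "in improving currently used risk assessment tools for MACE". One of the tools described there is the GRACE score: "It takes into account age, heart rate, systolic blood pressure, creatinine, abnormalities of ECG or cardiac enzymes, and signs of heart failure".

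Section 8.2 lists what the registry merge will supply: "namely data on patient anthropometrics, cardiovascular history, indication for and interventions of the index PCI, comorbidities and cardiovascular risk factors". Section 4.1 describes the sample: "Approximately 800 consecutive patients after PCI who are informed about different forms of CR are recruited for this study". Staged PCI is excluded, but nothing restricts enrolment to acute or to elective procedures.

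**The concern.** The gain from a new marker depends on what is already in the comparator. Whether the PCI was acute or elective is known at discharge, before any step is counted. If it also predicts MACE and is associated with walking in the first two weeks, steps partly stand in for it whenever it is left out. The NRI and AUC gain then mix the contribution of steps with that of indication, and the claim of an independent predictor becomes harder to defend.

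At stake is the study's practical message: whether step counting tells the clinician something beyond what the chart already holds.

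**Working it through.** **Is indication really outside the model?** Section 5.1 and the synopsis define the model by a list, and indication is not in it. Reading it into cardiovascular history does not fit section 8.2, which lists the two as separate items. The cardiac rehabilitation comparison in section 5.1 is adjusted for unspecified confounders and so has room for indication. The primary model has no such clause.

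**Does indication vary here?** Section 4.1 sets no restriction. Section 2 describes the self-report study, which also supplies the planning effect, as one in patients after elective PCI. A covariate set adequate there need not be adequate in a mixed cohort.

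**The plan's own figures.** With hazard ratio 2.66, two-sided 0.05 and 80% power, the Schoenfeld formula for two equal groups gives 4 × (1.960 + 0.842)² / (ln 2.66)² = 32.8, so 33 events. Doubling gives 66; 66 / 0.08 = 825 patients; 825 / 600 × 12 = 16.5 months. All reproduce, and none changes here.

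**Size.** The documents give no base-model AUC, no effect of indication on MACE and no steps by indication, so the size can only be illustrated. Assumptions of a logistic simulation with 200,000 patients per scenario:

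- MACE 8% (section 5.1); 50% acute (assumed).
- One composite base predictor, log odds ratio 0.6 per SD, correlated −0.3 with steps and independent of indication (assumed). Base AUC without indication is about 0.69 when steps have an effect.
- Step effect 0.385 log odds per SD. The outer-quartile means of a normal variable lie about 2.54 SD apart, and ln 2.66 / 2.54 = 0.978 / 2.54 = 0.385. This treats the planning hazard ratio as an odds ratio.
- Odds ratio of acute indication for MACE 1.5 or 2.0, and a step difference of −0.5 to +0.5 SD in acute patients (assumed).

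AUC gain from steps:

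| Odds ratio, acute | Steps in acute (SD) | Base without indication | Base with indication | Ratio |
|---|---|---|---|---|
| 1.5 | −0.5 | 0.0279 | 0.0189 | 1.48 |
| 1.5 | −0.25 | 0.0274 | 0.0220 | 1.25 |
| 1.5 | 0 | 0.0205 | 0.0197 | 1.04 |
| 1.5 | +0.25 | 0.0215 | 0.0236 | 0.91 |
| 2.0 | −0.5 | 0.0332 | 0.0184 | 1.80 |
| 2.0 | −0.25 | 0.0265 | 0.0183 | 1.45 |
| 2.0 | 0 | 0.0239 | 0.0214 | 1.12 |
| 2.0 | +0.25 | 0.0166 | 0.0193 | 0.86 |
| 2.0 | +0.5 | 0.0144 | 0.0211 | 0.68 |

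Allowing a weaker step effect as well (0.2 log odds per SD, an odds ratio of 0.82) widens the ratios to about:

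- 1.25 to 2.5 if acute patients walk 0.3 to 0.5 SD less;
- 1.0 to 1.2 if steps do not differ;
- 0.64 to 0.90 if acute patients walk 0.3 SD more.

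If indication has no effect on MACE (odds ratio 1), the two gains are about equal.

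**No true step effect.** Over the assumed ranges, the spurious AUC gain is at most about 0.0015 (0.0018 in the 200,000-patient run at odds ratio 2.0 and −0.5 SD, a difference within simulation error). Only at an odds ratio of 3 does it reach about 0.004.

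NRI was not simulated; the figures concern the AUC gain alone.

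**The case against.** The strongest defence is that the analysis matches the hypothesis as worded. Section 3.1 claims a contribution beyond traditional risk factors, section 5.1 uses that comparator, and the source study also measured reclassification beyond traditional risk factors. That stands: the plan does not contradict itself on this point. It does not settle the matter, because section 2 sets out to improve current risk tools, and one it describes includes acute-presentation items that the planned base model does not name.

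It can also be said that the covariates are given only as broad groups and that the list in section 8.2 describes a data merge, not model terms. An analyst might therefore include indication anyway. That is possible, but nothing in the plan calls for it.

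Three stronger readings are tempting, and the documents support none of them:

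- *The added value is overstated.* No section says how indication relates to steps or to MACE, and the table shows that the sign reverses if acute patients walk more.
- *The overstatement is 1.5- to 3-fold.* Such ratios arise with age alone as the base model and a step odds ratio of 0.82 per SD (0.0171 / 0.0112 = 1.5; 0.0259 / 0.0084 = 3.1), and only when acute patients are assumed to walk less. The plan's base model is richer than age, and its planning effect is larger.
- *Procedural details of the index PCI must be in the model too.* They are also in the merge, but nothing in the documents or the calculation shows that leaving them out matters.

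**Conclusion.** The point holds as a possible mis-statement of the primary measure, in a direction that the documents do not determine. The omission is clear from the SAP's own text. Distortion of substance requires that indication predicts MACE and differs in early steps. When steps do not differ, the ratio stays at 1.0 to 1.2.

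Even then, the omission mainly rescales a gain that exists and creates almost none from nothing. All sizes rest on assumed inputs and on a simplified base model with indication independent of its other covariates. If those covariates already carry part of the effect of indication, the distortion would be smaller. The point ranks as a cheap improvement; it does not invalidate the primary analysis.

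**What to change.** In section 5.1 and the synopsis, add the indication for the index PCI (acute or elective) to the base model. Report the NRI and AUC gain of steps over that model as the primary result, and give the model without indication as a sensitivity analysis. Fix this before the outcome data are merged, so that the comparator is not chosen on results.

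The cost is a change of wording and one more parameter against about 66 expected events, using data already in the planned merge. The sample-size figures stay as they are. The reported gain may turn out less favourable.
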